**Table 8-3 Karnofsky/Lansky Performance Scales**

Karnofsky Scale (age $\geq$ 16 years)		Lansky Scale (age $<$ 16 years)	
Able to carry on normal activity and to work; no special care needed.		Able to carry on normal activity; no special care is needed	
100	Normal no complaints; no evidence of disease	100	Fully active
90	Able to carry on normal activity; minor signs or symptoms of disease	90	Minor restriction in physically strenuous play
80	Normal activity with effort; some signs or symptoms of disease	80	Restricted in strenuous play, tires more easily, otherwise active
Unable to work; able to live at home and care for most personal needs; varying amount of assistance needed.		Mild to moderate restriction	
70	Cares for self; unable to carry on normal activity or to do active work	70	Both greater restrictions of, and less time spent in active play
60	Requires occasional assistance, but is able to care for most of his personal needs	60	Ambulatory up to 50% of the time, limited active play with assistance/supervision
50	Requires considerable assistance and frequent medical care	50	Considerable assistance required for any active play, fully able to engage in quiet play

Karnofsky Scale (age $\geq$ 16 years)		Lansky Scale (age $<$ 16 years)	
Unable to care for self; requires equivalent of institutional or hospital care; disease may be progressing rapidly.		Moderate to severe restriction	
40	Disabled; requires special care and assistance	40	Able to initiate quiet activities
30	Severely disabled; hospital admission is indicated although death not imminent	30	Needs considerable assistance for quiet activity
20	Very sick; hospital admission necessary; active supportive treatment necessary	20	Limited to very passive activity initiated by others (e.g. television)
10	Moribund; fatal processes progressing rapidly	10	Completely disabled, not even passive play
0	Dead	0	Unresponsive

#### 8.4.1 Laboratory evaluations

All abnormal lab results must be evaluated for criteria defining an adverse event and reported as such if the criteria are met. For those lab adverse events, repeated evaluations are mandatory until normalization of the result(s) or until the result is no longer considered to be clinically significant.

Clinically notable laboratory findings are defined in [Appendix 2](#).

**Table 8-4 Laboratory Assessments**

Test Category	Test Name
Hematology	Hematocrit, Hemoglobin, MCH, MCHC, MCV, Platelets, Red blood cells, White blood cells, RBC Morphology, Differential (Basophils, Eosinophils, Lymphocytes, Monocytes, Neutrophils, Bands, Other (absolute value preferred, %s are acceptable)) Assessment will be done locally
Chemistry	Albumin, Alkaline phosphatase, ALT, AST, Gamma-glutamyl-transferase (GGT), Bicarbonate, Calcium, Magnesium, Phosphorus, Chloride, Sodium, Potassium, Creatinine, Creatinine kinase, Direct Bilirubin, Indirect Bilirubin, Total Bilirubin, or Urea Assessment will be done locally
HIV & Hepatitis B & C testing	EBV, HIV, HbsAg, HBsAb, HBcAb, HCVAb Assessment will be done locally
Serum immunoglobulin levels (IgG, IgA, IgM)	IgG, IgA, IgM Assessment will be done locally
CTL019 PK	CTL019 PK by q-PCR and/or flow cytometry (peripheral blood) [REDACTED] [REDACTED] [REDACTED] [REDACTED]

Test Category	Test Name
B&T cells by Flow cytometry	CD4, CD3, CD8, CD19, CD16+56, CD3+4+8, CD4/CD8 Ratio, CD3/CD19 Ratio [REDACTED]
Pregnancy Test	Serum pregnancy test performed at Screening, and Pre LD Chemo (Day -14 to Day -2) if applicable, D1 (Pre Infusion), End of Study (Month 12) Urine pregnancy test performed at D28, M3, M6. A serum pregnancy test can be performed instead of a urine pregnancy test at investigator discretion. Assessment will be done locally
Rapid Influenza Test	Assessment will be done locally

#### **8.4.2      Electrocardiogram (ECG)**

Not Applicable

##### **8.4.2.1    Cardiac imaging - MRA (magnetic resonance angiography), MUGA (multiple gated acquisition) scan or echocardiogram**

Not applicable

##### **8.4.2.2    Cardiac enzymes**

Not applicable

#### **8.4.3      Other safety evaluations**

##### **Chest X-ray**

Not applicable

##### **Imaging**

Not applicable

#### **8.4.4      Appropriateness of safety measurements**

The safety assessments selected are standard for this indication/subject population.

#### **8.5        Additional assessments**

##### **8.5.1      Clinical Outcome Assessments (COAs)**

###### **Clinician Reported Outcomes (ClinRO)**

Not applicable

###### **Patient reported outcomes (PRO)**

###### **Pediatric Quality of Life inventory – Version 4 (PedsQL™ 4.0)**

Not applicable  
[REDACTED]

### **Trial Feedback**

Not applicable

### **Performance Outcomes (PerfO)**

Not applicable

### **Observer Reported Outcomes (ObsRO)**

Not applicable

### **Proxy Reported Outcomes**

Not applicable

### **8.5.2 Pharmacokinetics**

PK samples will be collected at the visits defined in the Assessment Schedule ([Table 8-1](#)). Follow instructions outlined in the central laboratory manual regarding sample collection, numbering, processing, and shipment. See the potential use of residual samples for more information.

[figure not shown]
In order to better define the PK profile, the timing of the PK sample collection may be altered based on emergent data.

The number of samples/blood draws and total blood volume collected will not exceed those stated in the protocol.

Pharmacokinetic (PK) samples will be obtained and evaluated in all subjects.

**Table 8-5 CTL019 pharmacokinetics by q-PCR in peripheral blood collection log**

Dose Number Infusion	Day*	Scheduled Time Point*	Tisagenlecleucel Dose Reference ID	PK 1 Tisagenlecleucel Sample No	Sample Volume
2	D1	Pre-dose	201	201	3 mL
2	D28		201	202	3 mL
2	M3		201	203	3 mL
2	M12		201	204	3 mL
2	Unscheduled		201	205	3 mL

#### **8.5.2.1 Pharmacokinetic blood collection and handling**

Refer to the Laboratory Manual for detailed instructions for the collection, handling, and shipment of PK samples.

#### **8.5.2.2 Analytical method**

The assays to be utilized for various PK/biomarker assessments include q-PCR assay to detect CTL019/4-1BB+ cells (transgene copies/microgram DNA) in peripheral blood and other tissues and flow cytometric analysis to detect CTL019 positive cells. Details of sample collections for these assays will be provided in the Central Laboratory Manual.

#### **8.5.3 Biomarkers**

Sample(s) will be collected at the time point(s) defined in the Assessment Schedule ([Table 8-1](#)).

Follow instructions for sample collection, numbering, processing, and shipment provided in the Central Laboratory Manual.

Quantification of biomarker expression in baseline liquid biopsies will be performed by a central laboratory using quantitative immuno-fluorescence and/or other methods (flow cytometry).

The effect of tisagenlecleucel therapy on B cell levels will be measured in peripheral blood to assess on-target effect on these CD19 positive cells.

#### **8.5.3.1 Additional biomarker assessments**

Not applicable

#### **8.5.4 Imaging**

Not applicable

#### **8.5.5 Other Assessments**

No additional tests will be performed on subjects entered into this study.

### **9 Study discontinuation and completion**

#### **9.1 Discontinuation**

##### **9.1.1 Discontinuation of study**

Patient's participation in the study may be discontinued if, in the investigator's opinion, its continuation would be detrimental to the patient's safety.

Subjects who discontinue from study should NOT be considered withdrawn from the study before they return for the EOS assessments indicated in [Section 9.2 Study completion and post-study treatment](#). If they fail to return for these assessments, every effort (e.g. telephone, email, letter, etc.) should be made to contact them.

Discontinuation of study for a subject occurs when study is stopped earlier than the protocol planned duration, and can be initiated by either the subject or the investigator.

Study participation must be discontinued under the following circumstances

- Subject/guardian decision
- Investigator Decision
- Pregnancy
- Use of prohibited treatment as per recommendations in [section 6.2.2](#)
- Any situation in which study participation might result in a safety risk to the subject
- Any laboratory abnormalities that in the judgment of the investigator, prevents the subject from continuing participation in the study

If discontinuation occurs, the investigator should make a reasonable effort to understand the primary reason for the subject's premature discontinuation of study and record this information.

Subjects who discontinue the study or who decide they do not wish to participate in the study further should NOT be considered withdrawn from the study UNLESS they withdraw their consent (see [section 9.1.2/Withdraw of informed consent section](#)). **Where possible, they should return for the assessments indicated** in the assessment schedule. If they fail to return for these assessments for unknown reasons, every effort (e.g. telephone, e-mail, letter) should be made to contact the subject/pre-designated contact as specified in the lost to follow-up section. This contact should preferably be done according to the study visit schedule.

If the subject cannot or is unwilling to attend any visit(s), the site staff should maintain regular telephone contact with the subject, or with a person pre-designated by the subject. This telephone contact should preferably be done according to the study visit schedule.

If the subject is willing, at a minimum, in abbreviated visits, the following data should be collected at clinic visits or via telephone/email contact:

- new/concomitant treatments
- adverse events/Serious Adverse Events

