#### **Medication restrictions prior to tisagenlecleucel infusion**

1. **Steroids:** Therapeutic doses of steroids must be stopped >72 hours or 5 half-lives, whichever is greater, prior to tisagenlecleucel infusion. However, the following physiological replacement doses of steroids are allowed: <12 mg/m^2/day hydrocortisone or equivalent
2. **Steroids or other immunosuppressant drugs** should NOT be used as pre-medication for tisagenlecleucel therapy (refer to [Section 6.2.1/ Pre-Infusion Evaluation](#)) or following tisagenlecleucel infusion, except as required for physiological glucocorticoid replacement therapy, or under life threatening circumstances. Use of steroids with blood product administration should be avoided just prior to and following tisagenlecleucel if possible or at least minimized.
3. **CNS disease prophylaxis or intrathecal therapy** must be stopped > 1 week prior to tisagenlecleucel infusion (e.g. intrathecal methotrexate)
4. **Radiation therapy** must be stopped > 2 weeks prior to tisagenlecleucel infusion
5. **Investigational therapies** must not be used at any time while on study until the first progression following tisagenlecleucel infusion
6. **Live vaccines** must not be used in tisagenlecleucel recipients for at least 6 weeks prior to lymphodepletion and during tisagenlecleucel treatment until immune recovery
7. **Granulocyte macrophage-colony stimulating factor** has the potential to worsen CRS symptoms and is not recommended during the first 3 weeks after tisagenlecleucel infusion or until CRS has resolved. Short acting granulocyte colony stimulating factor (G-CSF)

should not be given 72 hours prior to tisagenlecleucel infusion and long acting G-CSF should not be given 10 days prior to tisagenlecleucel infusion.

8. **Antiproliferative therapies**, other than lymphodepletion including low dose daily or weekly maintenance chemotherapy) should not be used within 2 weeks prior to infusion.
9. Short acting drugs used to treat primary disease (e.g. hydroxyurea) must be stopped > 72 hours prior to tisagenlecleucel.

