**Table 6-2 CRS management**

CRS severity	Symptomatic treatment	Tocilizumab	Corticosteroids
Mild symptoms requiring symptomatic treatment only e.g. low fever, fatigue, anorexia, etc.	Exclude other causes (e.g. infection) and treat specific symptoms with e.g. antipyretics, anti-emetics, anti-analgesics, etc. If neutropenic, administer antibiotics per local guidelines	Not applicable	Not applicable
Symptoms requiring moderate intervention: - high fever - hypoxia - mild hypotension	Antipyretics, oxygen, intravenous fluids and/or low dose vasopressors as needed.	If no improvement after symptomatic treatment administer tocilizumab i.v. over 1 hour: - 8 mg/kg (max. 800 mg) if body weight $\geq$ 30 kg - 12 mg/kg if body weight $<30$ kg If no improvement, repeat every 8 hours (max total of 4 doses)*	If no improvement within 12-18 hours of tocilizumab, administer a daily dose of 2 mg/kg i.v. methylprednisolone (or equivalent) until vasopressor and oxygen no longer need, then taper.*
Symptoms requiring aggressive intervention: -hypoxia requiring high-flow oxygen supplementation or - hypotension requiring high-dose or multiple	High-flow oxygen Intravenous fluids and high-dose vasopressor/s Treat other organ toxicities as per local guidelines		

CRS severity	Symptomatic treatment	Tocilizumab	Corticosteroids
vasopressors			
Life-threatening symptoms: - hemodynamic instability despite i.v. fluids and vasopressors - worsening respiratory distress - rapid clinical deterioration	Mechanical ventilation Intravenous fluids and high-dose vasopressor/s Treat other organ toxicities as per local guidelines		

\* If no improvement after tocilizumab and steroids, consider other anti-cytokine and anti-T-cell therapies. These therapies may include siltuximab (11 mg/kg i.v. over 1 hour), high doses of steroids (e.g. high dose methylprednisolone or equivalent steroid dose according to local ICU practice) cyclophosphamide, anti-thymocyte globulin (ATG) or alemtuzumab.

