#### **Management**

- If the neurological event is concurrent with CRS please refer to [Table 6-2](#). CRS algorithm table for treatment recommendation.
- Consider anti-seizure medications (e.g. levetiracetam) for patient at high risk (prior history of seizure) or administer in the presence of seizure
- For encephalopathy, delirium or associated events: appropriate treatment and supportive care should be implemented as per local standard of care. In worsening events, consider a short course of steroids ([Teachey, et. al 2018](#), [Neelapu et. al 2018](#)).

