#### **6.6.2.8 Hypersensitivity including acute infusion reactions**

Patients should be monitored for signs and symptoms of hypersensitivity following initiation of tisagenlecleucel infusion and treated appropriately. Tisagenlecleucel is contraindicated in patients with known hypersensitivity to tisagenlecleucel or to any component of the product formulation.

As appropriate, prophylactic medications should be administered to minimize the risk of immediate hypersensitivity including acute infusion reactions. It is recommended to pre-medicate all patients with acetaminophen (paracetamol) and diphenhydramine or another H1 antihistamine within approximately 30-60 minutes prior to tisagenlecleucel infusion. These medications can be repeated every 6 hours as needed. Non-steroidal anti-inflammatory medication may be prescribed for fever not responding to acetaminophen. Steroids should not be used for premedication. Systemic corticosteroids should only be used for severe conditions.

Should emergency treatment be required in the event of life-threatening hypersensitivity or other infusion-related reaction, supportive therapy such as oxygen and drug treatment should be given according to local institutional guidelines. Patients should be evaluated and carefully monitored until complete resolution of signs and symptoms.

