#### **6.6.2.11 Aggravation of graft versus host disease (GVHD)**

GVHD can be severe but can be controlled with steroids and other immunosuppressants as per local standard of care.

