## 8 Visit schedule and assessments

The Assessment Schedule ([Table 8-1](#)) lists all of the required assessments and it is indicated with an "X" at each visit when they are to be performed. All data obtained from these assessments must be supported in the patient's source documentation. No CRF will be used as a source document. The tables indicate which assessments produce data to be entered into the clinical database (D) or remain in source documents only (S) ("Category" column). Patients should be seen for all visits/assessments as outlined in the assessment schedule ([Table 8-1](#)) or as close to the designated day/time as possible. Missed or rescheduled visits should not lead to automatic discontinuation. Patients who prematurely discontinue the study for any reason should be scheduled for a visit as soon as possible, at which time all of the assessments listed for the final visit will be performed. At this final visit, all adverse events and concomitant medications should be recorded on the CRF.

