**Table 16-2 Concomitant Medication and Laboratory Reporting**

	Screening and Pre-treatment Period (ICF to LD chemo/ re-infusion )	Treatment and Follow-up Period (Starting from LD chemo / infusion , through Month 12 or discontinuation)	
	Inpatient/ICU OR Outpatient	Inpatient/ICU	Outpatient
Concomitant medications	Modified: Drugs:		All

	Screening and Pre-treatment Period (ICF to LD chemo/ re-infusion )	Treatment and Follow-up Period (Starting from LD chemo / infusion , through Month 12 or discontinuation)	
	Inpatient/ICU OR Outpatient	Inpatient/ICU	Outpatient
	
Record all of the following medications:
 
Anticytokine therapies (e.g. tocilizumab, or other)
 
Corticosteroids (including prophylactically for blood product administrations, physiologic replacement doses, high or stress doses, etc.)
 
Anti-seizure medications
 
Allopurinol, or non-allopurinol alternatives
 
Rasburicase
 
Immunoglobulin therapy
 
Any medication given therapeutically for an SAE
 
Vasopressors and cardiac inotropic agents (see below)
 
Narcotics and sedatives (see below)
 
Antineoplastic therapies (e.g. lymphodepleting chemotherapy)
 
Related to an AE or SAE defined as reportable for this period
 
Vasopressors and cardiac inotropic agents:
 
For dose, record only maximum daily rate (e.g. µg/kg/hr, mg/hr, etc.)
 
Narcotics and sedatives:
 
For dose, record only total daily dose
 
Blood products (e.g. red cells, platelets, FFP, cryoprecipitate):
 
Record all blood products, including prophylaxis
 
Electrolyte & vitamin replacement:
 
Record all electrolyte replacement if given for a clinically significant electrolyte disturbance and list these as an adverse event (AE).
 
Do not record prophylactic use of electrolyte or vitamin replacements
 
Do not record total parenteral nutrition (TPN) on concomitant medication CRF
 
Fluids:
 
Do not record fluid boluses and maintenance fluids
 
Antibiotics:
 
Record all antibiotics starting from day of infusion, even if given prophylactically
		

	Screening and Pre-treatment Period (ICF to LD chemo/ re-infusion )	Treatment and Follow-up Period (Starting from LD chemo / infusion , through Month 12 or discontinuation)	

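### Protocol Sections 6.2.2 and 9.1.1 do not exempt the methylprednisolone that Table 6-2 calls for in CRS short of life-threatening, so read literally those patients must be discontinued

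*Protocol*

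**What the plan says.** **The trigger.** Protocol Section 9.1.1 lists circumstances in which participation must be discontinued. One is "Use of prohibited treatment as per recommendations in" Section 6.2.2. No exception follows.

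**The restriction.** Section 6.2.2 item 2 says steroids and other immunosuppressants should not be used as pre-medication "or following tisagenlecleucel infusion, except as required for physiological glucocorticoid replacement therapy, or under life threatening circumstances". Item 1 caps physiological replacement at below 12 mg/m²/day of hydrocortisone or equivalent.

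**The CRS algorithm.** The corticosteroid column of Table 6-2 reads "If no improvement within 12-18 hours of tocilizumab, administer a daily dose of 2 mg/kg i.v. methylprednisolone (or equivalent"). The instruction begins in the moderate-intervention row (high fever, hypoxia, mild hypotension). Life-threatening symptoms have a separate row further down. Section 6.6.2.1 calls the algorithm a guideline that the investigator may modify.

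**Other adverse-event guidance.** These passages permit steroids without directing them:
- Section 6.6.2.2, neurological events: "In worsening events, consider a short course of steroids".
- Section 6.6.2.8, hypersensitivity: "Systemic corticosteroids should only be used for severe conditions".
- Section 6.6.2.11: "GVHD can be severe but can be controlled with steroids and other immunosuppressants as per local standard of care".

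**Data capture.** For the period through Month 12 or discontinuation, Table 16-2 asks sites to record "Corticosteroids (including prophylactically for blood product administrations, physiologic replacement doses, high or stress doses, etc".

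**After discontinuation.** Section 8 says "Patients who prematurely discontinue the study for any reason should be scheduled for a visit as soon as possible", with all final-visit assessments done then. Section 9.1.1 adds that such patients are not withdrawn unless they withdraw consent, should return for scheduled assessments where possible, and must be actively contacted if they do not.

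**The concern.** Only Section 6.2.2 opposes Section 6.6.2 head-on. A site can obey 6.6.2 and 9.1.1 together, but only by taking off study a patient who was treated as the protocol recommends.

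The timing is awkward for the primary endpoint. Section 4.5.1.1 puts CRS onset in almost all cases between days 1 and 10, and Table 8-1 places the first post-infusion flow cytometry and qPCR sample at Day 28. Discontinuation for CRS steroids would therefore usually come before any endpoint sample. From then on:
- Scheduled assessments are done only where possible (Section 9.1.1).
- For patients seen in abbreviated visits or by telephone, the minimum data are treatments and adverse events, with no B-cell or qPCR sample (Section 9.1.1).
- There is no replacement policy (Section 9.1.1.1).
- An unknown response counts as non-response (Section 12.4.3).

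Any endpoint loss by this route would lower the observed aplasia rate, and it would do so in patients with marked CRS. There is also a consistency problem. Sites that apply the text literally and sites that infer an exemption would handle identical patients differently.

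**Working it through.** **1. Do the exceptions in 6.2.2 item 2 cover the Table 6-2 dose?**

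| Exception | Covers Table 6-2 methylprednisolone? |
|---|---|
| Life-threatening circumstances | Only for the life-threatening row. The instruction starts at the moderate row. |
| Physiological replacement, below 12 mg/m²/day hydrocortisone equivalent | No, see below. |

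The dose per m² is 2 mg/kg × weight × potency ratio ÷ body surface area. Assumed, since the documents give none of these: a methylprednisolone-to-hydrocortisone ratio of 4 to 5, and body surface area = √(kg × cm / 3600).
- 15 kg, 100 cm: area 0.645 m²; 2 × 15 × 4 / 0.645 = 186 mg/m²/day.
- 60 kg, 168 cm: area 1.673 m²; 2 × 60 × 5 / 1.673 = 359 mg/m²/day.

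The conclusion does not depend on the ratio. Counted milligram for milligram, the smaller child receives 30 / 0.645 = 46 mg/m²/day, already well above 12.

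**2. Does the restriction reach past infusion?** Item 2 sits under a subheading about the period before infusion, but its own words extend to the time after it. So do items 5 and 7 in the same list, on investigational therapies and GM-CSF.

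**3. Is an exemption written anywhere?** Section 6.2.3 refers CRS and neurotoxicity management to REMS and institutional procedures and does not mention 6.2.2 or 9.1.1. Section 6.6.2.1 allows corticosteroids as indicated, also without a link. Table 16-2 expects high-dose steroids to be recorded, which suggests these patients were meant to stay on study, but it does not say so.

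**4. How much room does the planned design have?** Inputs from Protocol Sections 12.4.2 and 12.8: null rate 0.10, true rate 0.25, one-sided alpha 2.5%, at least 80% power, 49 evaluable patients.
- Rejection rule: the Clopper-Pearson 95% lower limit is 0.1024 at 10/49 and 0.0876 at 9/49, so at least 10 responders are needed. This agrees with SAP Section 2.6.2.
- Exact one-sided alpha: P(X ≥ 10 | 49, 0.10) = 0.0215.
- Power: P(X ≥ 10 | 49, 0.25) = 81.7%. The plan's figure of at least 80% reproduces.

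Let L be the share of would-be responders whose endpoint data are lost, so that they count as non-responders. The effective rate is 0.25 × (1 − L).

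| L (assumed) | Effective rate | Power |
|---|---|---|
| 0 | 0.2500 | 81.7% |
| 1% | 0.2475 | 80.6% |
| 2% | 0.2450 | 79.5% |
| 5% | 0.2375 | 75.9% |

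Power equals 80% at an effective rate of 0.24617, so L = 1 − 0.24617/0.25 = 1.53%. Expected responders are 49 × 0.25 = 12.25, and 1.53% of that is 0.19 of a patient.

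**5. What would the steroid route need to contribute?** Write L = s × m, where s is the share of would-be responders given such steroids and m is the share of those who then lose endpoint data. Power falls below 80% when m exceeds 0.01534/s:
- s = 5%: m above 31%.
- s = 10%: m above 15%.
- s = 21%: m above 7.3%.

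Both s and m are assumptions. The 21% is the grade 3 CRS rate after first infusion given in the Protocol's clinical safety summary (Section 1.1.5.2), used only as an illustrative high value. Section 4.5 expects a lower risk of severe CRS without overt relapse, and Section 6.6.2.1 reports prompt responses to tocilizumab in most subjects.

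**The case against.** The strongest opposing reading is that the protocol, taken whole, does not forbid these steroids. Item 2 uses advisory wording where most items in its list use mandatory wording. Section 6.1.3 states the same rule as a recommendation with a wider exception, for serious emergency, which could plausibly include CRS that has not responded to tocilizumab. Section 6.2.3 treats CRS management as rescue medication, and the glossary counts rescue therapy among treatment that may be needed or allowed on study. Specific adverse-event guidance would normally override a general restriction.

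This makes the intent fairly clear but does not remove the conflict. The 9.1.1 trigger is tied to the recommendations in 6.2.2, so advisory wording does not take item 2 outside it. The serious-emergency phrase is a second, different threshold and does not touch 9.1.1. Section 6.2.3 is only a pointer.

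Two further objections stand:
- No loss of endpoint data has been shown. Discontinued patients remain to be contacted and sampled where possible, and the final visit in Table 8-1 includes both assays.
- The power thresholds reflect the thin margin at n=49 and the discreteness of the exact test. Any loss from any cause would have the same effect, so they are not evidence about steroids.

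It is also correct that nothing in the current analysis depends on this. SAP Sections 2.6 and 2.6.2 list data for 5 enrolled patients and run no test.

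**Conclusion.** The concern holds as a minor defect in the protocol text. Read literally, Sections 6.2.2 and 9.1.1 require discontinuation of a patient given Table 6-2 methylprednisolone for CRS short of life-threatening, and nothing written exempts that patient. The conflict is clearest for CRS. For neurological events, hypersensitivity and GVHD the guidance is permissive only.

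The endpoint loss cannot be sized from the documents, which give neither a steroid rate nor an attendance rate after discontinuation, and it may be nil. What can be said is that the planned design tolerated a loss of only about 1.5% of would-be responders, from any cause, before power dropped below 80%. That rests on n=49, a true rate of 25% and lost cases counted as non-responders. The listings under the current SAP do not change; the point concerns the protocol text, the planned design and any reuse of this wording.

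**What to change.** In Section 9.1.1, state that treatment given for adverse events under Section 6.6.2 does not trigger discontinuation for prohibited treatment. Add the same exception to Section 6.2.2 item 2. These patients then stay on the Day 28, Month 3 and Month 12 B-cell and qPCR schedule.

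The cost is two sentences, with no extra visits or samples and no change to any analysis. The Full Analysis Set needs no edit, since it already includes every re-infused patient. Which steroid threshold is clinically right is for the sponsor's clinical team; the exemption only settles who stays on study.
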